### **3.15.3 Intervention for nurses**

The purpose of this program was to ensure all nurses(n=47) gained knowledge and experience on the KC technique, and promoted KC and breastfeeding to the mothers in the NICU for at least the first 3 months of their premature infant's life (corrected age). Pre-intervention test data (pretest) were collected by the researcher during the first meeting before conducting the intervention program (KC-EP). The implementation was carried out by the researcher to ensure consistency and equality in the delivery of KC-EP, this would enable the researcher to obtain a better understanding of the problems or difficulties that the nurses faced. For implementation purposes, this study appointed one senior staff nurse (working office hours) to assist the researcher in organizing the intervention process.

### **3.15.4 Meeting Place for the KC-EP Activities**

The meeting environment was comfortable, away from the noisy NICU environment. In the current KC-EP, the senior staff nurse in charge was given the responsibility of providing the nurses with the brief aim of the intervention program and choosing an appropriate time for the intervention session based on the schedules (Appendix J&K). The KC-EP time schedule for nurses' meetings and the instruments used for nurses are shown in Table 3.3.

### **3.15.5 The First Meeting**

The first meeting was held with the nurses to ensure that they had some perception, knowledge, and practice of KC. The researcher went through the educational information based on the developed KC-EP. The implementation of the KC-EP and the purpose of all the questionnaires were carefully explained during the first meeting. Nonetheless, one of the senior nurses who was working office hours was not directly involved in the implementation of the KC-EP; she was responsible for planning, scheduling, and verifying the date of the first meeting and notifying the researcher for post-intervention schedule. It was the role of the researcher to ensure that the KC-EP provided was accurate and given equally to all nurses, and to collect the data at the first meeting and then post-intervention (Table 3.3). During this meeting, the researcher and the nurses discussed openly any matters or problems faced by the nurses regarding KC implementation and how to promote breastfeeding. All of the nurses' inquiries were addressed accordingly. The nurses were taught about the theory of the KC technique and how to perform KC based on the KC-EP in order to increase the mother's role, knowledge and skills in caring for her premature. The KC-EP session involved 47 nurses working in rotating shifts. However, full-day sessions were conducted over the weekend. Each session involved 12 to 15 nurses, depending on their availability and shift duty. This was for the nurses to acquire similar awareness, knowledge, skills and attitudes before being taken to the mothers. The theory was delivered in four sessions and conducted twice a week (Friday and Sunday). All nurses on the evening shift were advised to participate in the morning session from 8.00 am till 12.00 noon, while those on the afternoon shift were advised to join in the afternoon session from 2.00 pm to 6.00 pm. The practical session was conducted every Monday, Wednesday, Thursday and Saturday from 8.00 am to 5.00 pm. The practical sessions encompassed all aspects of the data collection process, including obtaining informed consent, and enhancing usual communication activities between mothers and nurses. Premature baby mannequins were used as a teaching aid to demonstrate the KC

procedures until the nurses were skillful enough to perform proper KC gently, safely and effectively for all the skill steps required. A video on the KC procedure (standing and sitting transfers of KC) was played to guide the nurses in demonstrating the sitting and standing transfers. The researcher explained the KCPR booklet to the nurses and went through the booklet with them to emphasize its significance. A checklist was prepared by the researchers to evaluate the KC skill steps and the explanations on KC benefits before the procedure was implemented. Learning materials, such as leaflets and flip charts (English and Malay versions), were prepared by the researchers as teaching aids.

The entire program was allocated only 8 hours per session due to the nurses' workload. The researcher also sent reminders in the form of short notes to the nurses through WhatsApp (4th day) to ensure the nurses were alerted about sitting for the posttest on the 7th day post-intervention according to their schedule.

### **3.15.6 Short Message Via WhatsApp.**

To ensure each nurse's awareness of KC implementation and the date of the post-intervention test, the researcher sent a short message via WhatsApp to the nurses. This was a reminder for the nurses to perform return demonstrations of the KC (standing and sitting transfers) program goals to build up their personal beliefs and educate them on how to carry out KC and how to encourage breastfeeding for premature infants.

**Table 3.3: Schedule for Intervention and Instrument (KC-EP) for the Nurses**

Days/ Weeks	Pre - Intervention		Post - Intervention		Person in charge		
	Instrument	Activities	Instrument	Activities			
Day 1	Simple Orientation + KCQs (QII)	First Meeting KC-EP (Theoretical Session)	Practice on KC skills with the checklist provided for each of the procedure steps for all the nurses. i) standing & ii) sitting transfers	Short Message: WhatsApp	Researcher		
Day 2	Routine Ward Activities						
Day 3							
Day 4							
Day 5							
Day 6							
Day 7	KCQs(QII)	Second Meeting (Practical Session) Demonstration on KC	Researcher				

*KCQ=Kangaroo Care Questionnaire; QII=Questionnaire for nurses; KC-EP=Kangaroo Care Educational Programme; KC=Kangaroo care.*

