### **3.16 Data Collection Method**

There were three phases to this study: Phase I, Phase II, and Phase III. Phases included:

i)In phase, I, the data ( $T_0$ ,  $T_1$ , and  $T_2$ ) for the control group of mother-infant dyads was collected within six months until the data met the requirements of the study. Data collection for the control group's mother-infant dyads started in early February 2018, and continued until the end of July 2018. Assessment of function in routine clinical practices in the control group of mother-infant dyads and outcomes of premature infants was recorded in the KCPR booklet provided for the control group of mothers within the stipulated time and then analysed.

ii)In phase II, one group pretest-posttest for nurses' data collection process was conducted 2 months after the control group of mothers' data collection was completed. The data collection for nurses and the intervention commenced in early August 2018 and continued to the end of September 2018. Quantitative data (Questionnaire II) were collected at pretest, and one week after the structured KC-EP was conducted for nurses the posttest data were analyzed. The structured KC-EP for nurses included knowledge, skills, and attitude prior to KC guidelines and protocol. The specific aims were to educate nurses in the content areas noted above. The reasons for implementing a neonatal KC protocol for mother-infant dyads were generally considered in terms of the method of holding the premature infant directly, breastfeeding rates and looking at the effects of KC outcomes.

iii) In phase III, the data ( $T_0$ ,  $T_1$ , and  $T_2$ ) for the experimental group of mother and premature infant were collected within seven months. In the experimental group, data collection for mother-infant dyads began in early October 2018 and was completed by the end of April 2019. The KC-EP for mothers was conducted by the nurses in the NICU for them to implement KC with their premature infants. The structured KC-EP was comprised of theory and practical sessions to fulfill the objectives of this study. The post-intervention assessment

of quantitative data (Questionnaire I) on mother-infant dyad compliance and outcomes of KC implementation (KCPR) commenced from the premature infant's recruitment day. The data was plotted to begin from the inclusion criteria age until 3-months-old corrected age.

[figure not shown]

Figure 3.2: Flow Chart Showing the Three Phases of Data Collection

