All 47 nurses needed to demonstrate KC skills, attitudes, and knowledge for practical evaluation and assessment. The knowledge, skills, and attitudes of nurses towards the implementation of KC were observed during the practical return-demonstration session to improve the quality care of preterm infants. The current research attempted to determine whether the nurses were more likely to support KC for the mother of a preterm infant. The marks were classified as pass or fail. The nurses received one (1) accredited certificate related to the KC course upon completion of the structured KC-EP course evaluations. A 6-point Continuous Professional Development (CPD) certificate recognized by the Malaysian Nursing Board was issued to all nurses attending the KC-EP; the KC-EP on knowledge, attitude, and skills was passed successfully. Examples of the KC-EP schedules for nurses are shown in (Appendix I & J). All of the data collected at the pretest was intended to assess nurses' previous knowledge on KC before they were introduced to the KC technique in the NICU setting. The questionnaire was collected before the KC-EP was delivered. The posttest for nurses was conducted on the 7th day after the KC intervention program(KC-EP). The nurses also answered the same set of questions in Questionnaire II and demonstrated their skills in relation to KC procedure: standing and sitting transfers with a checklist provided to evaluate their knowledge, skills and attitude regarding encouraging mothers to perform KC and continue breastfeeding,

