### **3.17.1 Nursing Outcome Variables**

The data for nursing outcomes were collected in Phase II, historical control data were collected through a retrospective nurse audit of knowledge and skills in relation to KC management practices and assessing data on KC implementation techniques among mothers with premature infants. The nurses' perception, knowledge, and practice in relation to KC implementation were assessed using a set of structured questions, Questionnaire I for nurses, via a pre-test and then reassessed in a 7th day post-test following the program.

The researcher briefed the nurses and invited them, through a verbal briefing to the head nurse in charge of the selected unit, to participate in the study. On the same day as the pre-test, the Questionnaire I was given to the nurses, with two consent forms. Name, identification code number and date of attendance of the nurses who attended were recorded in order to plan the follow-up date for the post-test. The returned questionnaire was given an identification code number to ensure confidentiality and privacy. The consent form, including the questionnaire, was stamped in the right top corner with the code number, starting with nurse 01(N01). When nurses declined to continue the study, they were told to contact the researcher to ask for a withdrawal. Upon receiving an application for withdrawal from the study, the researcher destroyed the questionnaire, which was submitted based on the code number. All nurses were instructed to sit for the post-test on the 7th day after the pretest. The nurses were instructed to complete Questionnaire I for the pretest, which took about 15 to 20 minutes to complete, without referring to any resources before the KC-EP for nurses was conducted. Nurses were asked to return the questionnaires upon completion, together with one copy of the informed consent document. All nurses were expected to keep one copy of the informed consent form in their records. On the 7th day, the nurses were told to answer the same set of questions that had been used in the pretest. It was anticipated that an interval of 7 days would enable the posttest group nurses to translate their theoretical expertise into action and gain experience in evaluating, managing, and promoting the implementation of KC and also breastfeeding for mother-infant dyads through hands-on practice in the NICU environment.

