Next, the researcher collected the group of participants from among the nurses, made them comfortable, and orientated them to the study. She then administered the structured quantitative-based Questionnaire II for nurses. All nurses were instructed not to interact with each other, and their doubts were clarified. The questionnaire took 10 to 15 minutes to complete; after completion the researcher asked the nurses to return the pre-test questionnaires as well as a copy of the informed consent form. All nurses were instructed to keep one copy of the informed consent form for their records. On the same day, nurses were asked to return the completed questionnaire to the researcher. Each questionnaire returned was given an identification code number to ensure confidentiality and privacy. For each set of questionnaires (pretest and post-test), the consent form and the questionnaire were labeled with a code number, beginning with N01 for the nurses, at the right top corner. The nurses' baseline data were gathered on demographic characteristics and KCQ tools (perception, knowledge and practice) regarding the KC technique. After the pre-test phase, the structured kangaroo care educational program (KC-EP) for nurses was conducted within two weeks for all  $n=47$  nurses. The program was delivered in English for the theory, and the practical

session included the showing of videos related to the KC transferring technique by the researcher. All nurses were informed to sit for the required post-test on the 7th day after the pretest phase and the KC-EP teaching module. The same structured Questionnaire I was administered at the post-test, and nurses were required to demonstrate the KC standing and sitting procedure. A checklist was provided for each nurse to assess her confidence and skills in relation to the KC technique. The collection of nurses' data lasted from 1st of August 2018 until the 30th of September 2018.

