### Part III : Practice on KC

**Instruction:** Please describe how comfortable are you to initiate KC on baby with the following items? Use the following scale:

5 = Very Comfortable

4 = Somewhat Comfortable

3 = Neither Comfortable Nor Uncomfortable

2 = Somewhat Uncomfortable

1 = Very Uncomfortable

No.	Statement	5	4	3	2	1
1	Baby with intravenous catheters.					
2	Baby during the perioperative period.					
3	Baby with endotracheal intubation.					
4	Baby with high-frequency rate or ventilator mode.					
5	Baby with nasal cannula oxygen (nasal prong).					
6	Baby with Nasal Continuous Positive Airway Pressure (NCPAP).					
7	Baby with percutaneous central lines.					
8	Baby with phototherapy treatment.					
9	Baby with Umbilical Arterial Catheters (UAC).					
10	Baby with Umbilical Venous Catheters (UVC).					
11	Baby with anotrope/vasopressors.					

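### The plan contradicts itself on when nurses sit the posttest relative to their practical training, and the Part III practice score measures only self-rated comfort, so it cannot support H3's claim about practice.

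*Combined protocol and SAP*

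**What the plan says.** Section 3.15.2 gives the nurses' programme as 4 hours of theory and 4 hours of practice, and describes two sessions, the second being the posttest. Section 3.15.3 places the pretest at the first meeting, before any teaching. Section 3.15.5 holds theory on Fridays and Sundays and practicals on Mondays, Wednesdays, Thursdays and Saturdays. Appendices I and J add Tuesday to the practical days.

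The posttest is dated in several ways:

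- Table 3.3 puts the repeat of Questionnaire II on Day 7, with "Second Meeting (Practical Session) Demonstration on KC".
- Section 3.17.1: "All nurses were instructed to sit for the post-test on the 7 th day after the pretest".
- Section 3.17: "The posttest for nurses was conducted on the 7 th day after the KC intervention program(KC-EP".
- Section 3.16, phase II: "one week after the structured KC-EP was conducted for nurses the posttest data were analyzed". The reminder text in section 3.15.5 also counts from the intervention.
- Another sentence in section 3.17, section 3.18 and Appendix J each name the pretest and the programme together.
- Appendix K labels its practical columns as posttest and practical combined, but also has a separate posttest column for after the 7th day.

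The purpose of the interval is given in section 3.17.1: "It was anticipated that an interval of 7 days would enable the posttest group nurses to translate their theoretical expertise into action", through hands-on work on the unit.

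The practice outcome is Part III of Questionnaire II (Appendix H), eleven items under the instruction "Please describe how comfortable are you to initiate KC on baby with the following items". Section 2.5.2 says that performance is recorded on a checklist at the posttest but that evaluating skills is outside the study's scope. For nurses, Table 3.4 plans analysis of mean scores only.

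**The concern.** The nurse component is a one-group before-and-after comparison in 47 nurses, so the posttest date defines what the change score means. A score taken on the day of the practical reflects the session itself. A score taken a week later also reflects attempts to use the technique on the ward, which is what section 3.17.1 wants the interval to provide. If the rule is undefined, or was applied differently to different nurses, the mean change averages over unknown amounts of experience, and without dates nobody can tell how much.

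The second problem does not depend on timing. H3 claims improved practice, but the only scored variable under that name is how comfortable a nurse says she would be. A rise in comfort could be reported as nurses doing more, or better, kangaroo care, and no planned analysis would support that.

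**Working it through.** The plan states no figure to reproduce. The check is calendar arithmetic on the stated weekdays.

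**Inputs.** Pretest and theory are on Day 1, a Friday or a Sunday (sections 3.15.3 and 3.15.5, Table 3.3, Appendix K). Practical days are those in section 3.15.5, with Tuesday added from Appendices I and J. I assume that each nurse attends one practical within the week after her theory session.

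**Formula.** Gap = posttest day − practical day.

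| Theory (Day 1) | Possible practical days | Gap if posttest is on Day 7 | Gap if posttest is on Day 8 |
|---|---|---|---|
| Friday | Sat 2, Mon 4, Wed 6, Thu 7 | 5, 3, 1, 0 | 6, 4, 2, 1 |
| Sunday | Mon 2, Wed 4, Thu 5, Sat 7 | 5, 3, 2, 0 | 6, 4, 3, 1 |

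Day 8 is included because Day 1 to Day 7 is only 7 − 1 = 6 elapsed days, so a full seven days after the pretest falls on Day 8. Adding Tuesday (Day 5 after a Friday, Day 3 after a Sunday) gives Day 7 gaps of 7 − 5 = 2 and 7 − 3 = 4, which leaves the ranges unchanged.

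**Results by reading.**

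1. Table 3.3 taken literally, with the only practical on Day 7: 7 − 7 = 0 days.
2. Posttest on Day 7, practicals on the listed weekdays: 0 to 5 days.
3. Posttest a full seven days after the pretest: 1 to 6 days.
4. Posttest seven days after the whole programme: 7 days for every nurse.

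The two starting points cannot be the same day. Theory and pretest fall on Friday or Sunday, and no practical is held on either day. A posttest seven days after the pretest is therefore always less than seven days after the end of a programme that includes the practical, so the sections that name both cannot be satisfied together.

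**Construct.** Section 1.7.9 defines nursing practice in terms of competence, confidence and responsibility in starting kangaroo care. Part III records comfort on a 1 to 5 scale, which at most covers confidence. Section 3.17 adds a pass/fail demonstration, but it is described only after training and does not appear in Table 3.4, so it gives no before-and-after comparison.

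**The case against.** The strongest reply is that the intended rule is clear and only some wording is loose. Three places count from the intervention, and on that rule every nurse has seven days. Section 3.17.1 itself puts the hands-on period before the posttest and says the posttest follows the programme. The layout of Table 3.3 is damaged in the extracted text: the reminder message sits in the Day 1 row although section 3.15.5 dates it to the 4th day. That same row contains "Practice on KC skills with the checklist provided for each of the procedure steps for all the nurses", so skills work is not confined to Day 7. The Day 7 demonstration may be assessment rather than teaching, since sections 3.17 and 3.18 include a checklist demonstration in the posttest and Appendices I and J label the practical hours as assessment.

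This stands as far as it goes. A reader might infer from Table 3.3 that practice is tested before nurses have had any hands-on period, or that half the programme (4 of 8 hours) is taught on the test day. The documents do not establish either; the same-day reading is one of several. Nor does section 3.18's statement that "the structured kangaroo care educational program (KC-EP) for nurses was conducted within two weeks for all" 47 nurses show unequal intervals, because that is the time to train the whole group. Any inequality comes from the weekday schedule and remains a possibility.

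A reader might also want a repeat questionnaire during phase III. Objective 3 asks only about before and after participation and makes no claim of lasting change, so its absence contradicts nothing.

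On the construct, section 3.10.1 does describe Part III as indicating confidence level and skills. The confidence part is fair. The skills part is not, because no item observes or asks what a nurse does.

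**Conclusion.** The point holds as a contradiction in timing and a mismatch between outcome and claim. Experience between the practical and the posttest is undefined, with 0 to 7 days all compatible with the text, and it may differ between nurses. The upper end is the reading with most direct support, and the lower end needs a literal reading of a damaged table. The ranges rest on the weekdays in section 3.15.5 and Appendices I and J, and on one practical per nurse in the week after theory.

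The limit on H3 rests on fewer assumptions. Part III is given at both pretest and posttest, so it can show a change in comfort. Under no timing can it show a change in practice.

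**What to change.** 1. Adopt one rule: each nurse sits the Questionnaire II posttest seven days after she completes the whole programme, practical included. Sections 3.15.5, 3.16 and 3.17 already count from the intervention.
2. Bring Table 3.3, Appendices J and K, and sections 3.15.2, 3.17, 3.17.1 and 3.18 into line, stating whether the Day 7 demonstration is teaching or assessment.
3. Report each nurse's actual practical and posttest dates. Section 3.17 says attendance dates were recorded, so this may need no new data.
4. Restate objective 3 and H3 so that Part III is reported as self-rated comfort or confidence in initiating kangaroo care, and draw no conclusion about practice from it.

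The cost is wording and one listing of dates for 47 nurses. Items 3 and 4 remain possible after data collection, provided the dates were kept. The downside is a narrower H3 conclusion.

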### **3.16 Data Collection Method**

There were three phases to this study: Phase I, Phase II, and Phase III. Phases included:

i)In phase, I, the data ( $T_0$ ,  $T_1$ , and  $T_2$ ) for the control group of mother-infant dyads was collected within six months until the data met the requirements of the study. Data collection for the control group's mother-infant dyads started in early February 2018, and continued until the end of July 2018. Assessment of function in routine clinical practices in the control group of mother-infant dyads and outcomes of premature infants was recorded in the KCPR booklet provided for the control group of mothers within the stipulated time and then analysed.

ii)In phase II, one group pretest-posttest for nurses' data collection process was conducted 2 months after the control group of mothers' data collection was completed. The data collection for nurses and the intervention commenced in early August 2018 and continued to the end of September 2018. Quantitative data (Questionnaire II) were collected at pretest, and one week after the structured KC-EP was conducted for nurses the posttest data were analyzed. The structured KC-EP for nurses included knowledge, skills, and attitude prior to KC guidelines and protocol. The specific aims were to educate nurses in the content areas noted above. The reasons for implementing a neonatal KC protocol for mother-infant dyads were generally considered in terms of the method of holding the premature infant directly, breastfeeding rates and looking at the effects of KC outcomes.

iii) In phase III, the data ( $T_0$ ,  $T_1$ , and  $T_2$ ) for the experimental group of mother and premature infant were collected within seven months. In the experimental group, data collection for mother-infant dyads began in early October 2018 and was completed by the end of April 2019. The KC-EP for mothers was conducted by the nurses in the NICU for them to implement KC with their premature infants. The structured KC-EP was comprised of theory and practical sessions to fulfill the objectives of this study. The post-intervention assessment

of quantitative data (Questionnaire I) on mother-infant dyad compliance and outcomes of KC implementation (KCPR) commenced from the premature infant's recruitment day. The data was plotted to begin from the inclusion criteria age until 3-months-old corrected age.

[figure not shown]

Figure 3.2: Flow Chart Showing the Three Phases of Data Collection

